6.4.4.14 Posterior Segment

Funduscopy (dilated)

The posterior segment will be examined using a slit lamp in combination with a 90D or "Superfield" or comparable lenses. The entire fundus should be assessed including optic disc, posterior pole including macula and peripheral retina. Any variations of the norm, defects or lesions should be documented.

 Implantdata Ophthalmic Products GmbH	Clinical Investigation Plan ARGOS-03	Revision C Page 36 of 67
---------------------------------------------------------------------------------------------------------------------------	-------------------------------------------------------	---------------------------------

Optical Coherence Tomography (OCT)

Posterior segment OCT will be used to assess both macular structures and the peripapillary nerve fiber layer (RNFL).

If available, it should be used the Heidelberg Engineering Spectralis Glaucoma-Module Premium Edition (Minimum rim width at Bruch membrane opening (BMO-MRW), RNFLT and macula). This should always be done on both eyes in order to compare study and fellow eyes.

Fundus Photography

Standard fundus photography will be performed at baseline D180 and then once a year to document potential changes to the interior surface of the eye, including the retina. Additionally, a photo of the optic nerve and nerve fiber layer will be performed in red-free illumination.

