**Table 1: Visit Schedule**

Visits	V01	V02	V03	V04	V05	V06	V07
Indicative Days (D)	D0	D180 +/- 3 wks	D360 +/- 3wks	D540 +/- 3wks	D720 +/- 3wks	D900 +/- 3wks	D1080 +/- 3wks
General							
Informed Consent	X						
Handout of the patient diary	X						
Demographics	X						
Past and current significant medical history	X						
Comparative measurements	X						
Check of the functionality of the Mesograph and Multiline Connector	X						
Confirmation of the correct function of the ARGOS-IO sensor	X						
Visual acuity (EDTRS)  (both eyes)	X	X	X	X	X	X	X
Perimetry (both eyes)	X	X	X	X	X	X	X
Concomitant medications	X	X	X	X	X	X	X
Eye related AEs/ADE/SAE/SADE	X	X	X	X	X	X	X
NEI VFQ-25	X		X		X		X
Device deficiency		X	X	X	X	X	X
Check patient diary for completeness		X	X	X	X	X	X
Anterior Segment (both eyes)							
External eye photography (Slit lamp)	X	X	X	X	X	X	X
Slit-lamp biomicroscopy	X	X	X	X	X	X	X
Optical coherence tomography 	X	X	X	X	X	X	X
Corneal endothelial cell density	X	X	X	X	X	X	X
Gonioscopy	X	X	X	X	X	X	X
Posterior Segment (both eyes)							
Funduscopy	X	X	X	X	X	X	X
Optical coherence tomography 	X	X	X	X	X	X	X
Fundus photography 	X		X		X		X
IOP measurement							
Goldmann Applanation (both eyes)	X	X	X	X	X	X	X
Pascal DCT (both eyes)	X	X	X	X	X	X	X
ARGOS-IO clinic	X	X	X	X	X	X	X
ARGOS-IO home 	X	X	X	X	X	X	X

The best corrected visual acuity will be determined after objective and subjective determination of refraction with the EDTRS chart.

Anterior segment OCT is performed to assess the central cornea thickness and to evaluate effects on change in chamber angle after implantation.

Posterior segment OCT is used to assess macular structures and the peripapillary nerve fibre layer thickness (RNFLT) and (if possible) BMO-MRW

The fundus should be photographed in order to document potential changes to the optic nerve (cup/disc ration) and nerve fibre layer (red-free illumination).

IOP-measurements will be performed in series of 2 GAT measurement (with difference more than 2mmHg, a third GAT-measurement is required) and 3 directly consecutive measurements with the ARGOS-IO system followed by 2 Pascal tonometry (with difference more than 2mmHg, a third DCT-measurement is required) and 3 directly consecutive measurements with the ARGOS-IO system.

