### 2.4.3 Secondary Objectives

The following secondary objective have been defined for this trial:

- Evaluation of patient compliance in intraocular pressure (IOP) self-monitoring
  - Daily self-measurements with the ARGOS-IO sensor should be done at least 4 times daily (morning, noon, afternoon, evening)

- Evaluation of the impact of IOP self-monitoring on glaucoma progression
  - Parameters to evaluate the glaucoma progression are visual field, cup/disc ratio, OCT of the optic nerve and the IOP
- Evaluation of incidences in glaucoma medication change
- Evaluation of the number of unscheduled visits due to self-measured increased IOP
  - The patients decide to come for a visit by their own due to any reason. This will be documented

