### 6.4 Secondary Performance Variables

The following secondary variables are planned to be evaluated:

- Glaucoma progression over the course of the study evaluated by change in
  - visual field
  - cup/disc ratio (horizontal and vertical)
  - OCT results for the optic nerve
  - IOP
- Number of changes in glaucoma medication
- Number of unscheduled visits due to self-measured increased IOP

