## 7.6 Evaluation of Secondary Variables

### Progression analysis

Summary statistics for raw values and change over time will be provided for visual field, cup/disc ratio and IOP (for all types of measurements) by eye and visit. Frequency tabulations (absolute and relative) will be prepared for OCT results for the optic nerve over the course of the study, by eye and visit. The denominator for the calculation of relative frequencies will be the number of subjects attending the respective visit.

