#### 8.2 Performance

- 8.2.1 Comparison of intraocular pressure measurements (IOP)
  - 8.2.1.1 IOP measurements with ARGOS-IO and comparators by visit
  - 8.2.1.2 Limits of agreement between IOP measurements with ARGOS-IO and comparators by visit
  - 8.2.1.3 Limits of agreement between IOP measurements with ARGOS-IO and comparators by subgroup and visit
- 8.2.2 Device malfunctions
  - 8.2.2.1 Summary of device malfunctions
  - 8.2.2.2 Summary of device malfunctions by subgroup
  - 8.2.2.3 Device malfunctions per 10 patient years
- 8.2.3 Glaucoma progression by visit
- 8.2.4 Change in glaucoma medication
  - 8.2.4.1 Summary of changes in glaucoma medication
  - 8.2.4.2 Changes in glaucoma medication per 10 patient years
- 8.2.5 Unscheduled visits due to self-measured increased IOP

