## Listings

12.2	Subject data listings
12.2.1	Disposition of subjects
12.2.1.1	Site numbers and principal investigators
12.2.1.2	Informed consent
12.2.1.3	Visit dates and discontinuation
12.2.2	Protocol deviations
12.2.3	Demographics and other patient characteristics
12.2.4	Medical history and concomitant diseases
12.2.4.1	Medical history
12.2.4.2	Concomitant diseases
12.2.5	Concomitant medications
12.2.5.1	Glaucoma medication
12.2.5.2	Other concomitant medications
12.2.6	Performance
12.2.6.1	IOP measurements by visit
12.2.6.2	Device malfunctions
12.2.6.3	Glaucoma progression by visit
12.2.6.4	Unscheduled visits
12.2.7	Safety data
12.2.7.1	Adverse events listing
12.2.8	Other data
12.2.8.1	Best corrected visual acuity by eye and visit
12.2.8.2	National Eye Institute Vision-related Quality of Life Questionnaire (NEI VFQ-25) by visit
12.2.8.3	Device deficiencies
12.2.8.4	Ophthalmic examinations
12.2.8.4.1	Abnormalities detected by slit-lamp microscopy by eye and visit

- 12.2.8.4.2 Abnormalities detected by funduscopy by eye and visit
- 12.2.8.4.3 Gonioscopy results by eye and visit
- 12.2.8.4.4 Other examinations
- 12.2.8.5 Position of IOL and ARGOS-IO pressure sensor by visit
- 12.2.8.6 Comparative measurements performed in the clinic between study end of ARGOS-01/ARGOS-02 and Visit 01 (GAT vs. ARGOS-IO)

The selection, naming and numeration of the listings is not mandatory but might be adapted in accordance with the described analyses in this SAP.

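### Glaucoma progression is defined as change in four parameters, but optic-nerve OCT gets only per-visit frequencies, which in general cannot show change within an eye

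*SAP*

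**What the plan says.** SAP 2.4.3 names the measures for the secondary objective on progression: "Parameters to evaluate the glaucoma progression are visual field, cup/disc ratio, OCT of the optic nerve and the IOP". SAP 6.4 turns them into variables under the lead-in "Glaucoma progression over the course of the study evaluated by change in", followed by the same four items.

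SAP 7.6 (Progression analysis) splits the four. For three it states: "Summary statistics for raw values and change over time will be provided for visual field, cup/disc ratio and IOP", by eye and visit. For the fourth: "Frequency tabulations (absolute and relative) will be prepared for OCT results for the optic nerve over the course of the study", also by eye and visit, with the subjects attending each visit as denominator.

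The table list in the SAP appendix has one progression heading, "8.2.3 Glaucoma progression by visit". Listing 12.2.6.3 carries the same title.

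On the scan itself, footnote 3 of SAP Table 1 reads: "Posterior segment OCT is used to assess macular structures and the peripapillary nerve fibre layer thickness (RNFLT) and (if possible) BMO-MRW". Protocol 6.4.4.14 names the same quantities for the preferred device: "Minimum rim width at Bruch membrane opening (BMO-MRW), RNFLT and macula".

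Protocol 7.2.5 covers the same four parameters. It plans change from baseline for continuous variables and, where this makes sense, shift tables for categorical ones.

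**The concern.** Progression is a statement about the same eye at two times. Frequencies by visit describe the group's status at each visit. They do not show which eyes moved, or in which direction, once eyes leave the study or readings reverse.

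OCT is not a marginal measure for this objective. Protocol 3.1 describes glaucoma as progressive thinning of the nerve fibre layer and the neuroretinal rim, and RNFLT and BMO-MRW measure those structures. Protocol 6.4.4.14 also asks for the scan in both eyes so that study and fellow eyes can be compared; comparing their progression needs change per eye.

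At stake is the descriptive result for one of four secondary progression variables. No hypothesis, error rate or sample size is affected.

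**Working it through.** There is no stated figure to reproduce. The check has three parts.

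**1. Definition against analysis**

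| Parameter in SAP 6.4 | Analysis in SAP 7.6 |
|---|---|
| Visual field | raw values and change over time |
| Cup/disc ratio | raw values and change over time |
| IOP | raw values and change over time |
| Optic-nerve OCT | frequencies by eye and visit |

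Four parameters are defined by change and three are analysed as change. Nothing elsewhere fills the gap. SAP 7.1 adds raw values to tables that already contain change. SAP 7.3.1 says how change is computed when it is analysed. SAP 8 declares only the change to the IOP agreement analysis.

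**2. What two visit counts can show**

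Assume a normal/abnormal field. Let

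- *n* = eyes at Visit 01; 26 is the maximum sample size (SAP 2.9);
- *a*, *b* = abnormal eyes at Visit 01 and Visit 07;
- *d* = drop-outs, who are not replaced (SAP 2.6), with data used as available (SAP 5.2);
- *L* = drop-outs who were abnormal at Visit 01;
- *R* = eyes abnormal at Visit 01 and normal at Visit 07.

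Of the *a* abnormal eyes, *a* − *L* − *R* are still abnormal at Visit 07, so among eyes assessed at both visits

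newly abnormal = *b* − *a* + *L* + *R*, with max(0, *d* − (*n* − *a*)) ≤ *L* ≤ min(*d*, *a*).

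The tables give *a* and *b*, but not *L* or *R*. The values of *a*, *b*, *d* and *R* below are assumptions; the documents give none. With *n* = 26:

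| *a* | *b* | *d* | *R* | Newly abnormal |
|---|---|---|---|---|
| 10 | 10 | 0 | 0 | 10 − 10 + 0 + 0 = 0 |
| 10 | 10 | 1 | 0 | 0 to 1 |
| 10 | 10 | 3 | 0 | 0 to 3 |
| 10 | 10 | 3 | 0 to 2 | 0 to 5 |
| 10 | 12 | 0 | 0 | 12 − 10 + 0 + 0 = 2 |
| 10 | 12 | 3 | 0 | 2 to 5 |

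For *d* = 3 and *a* = 10, *L* runs from max(0, 3 − 16) = 0 to min(3, 10) = 3, which gives the ranges shown. With no drop-outs and no reversals, the difference between the counts is the answer. If the field is numeric, frequencies give no mean change at all.

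**3. SAP against protocol (conditional)**

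SAP 1 says it elaborates protocol revision B; the protocol supplied is revision C. If revision B has the same text in 7.2.5, and RNFLT or BMO-MRW was recorded as a number, then SAP 7.6 drops a planned change from baseline. SAP 2.11 asks for such a change to be justified in the SAP text, and neither 7.6 nor 8 does so for OCT. If only categories were recorded, the qualifier in 7.2.5 leaves room for plain frequencies, and only the mismatch in part 1 remains.

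**The case against.** The best defence is that the field is probably categorical. SAP 7.1 gives summary statistics to quantitative variables and counts to categorical ones, and 7.6 treats OCT in the second way, as 7.8 treats funduscopy and gonioscopy. Central corneal thickness, which the protocol assesses by anterior-segment OCT, does get change over time in 7.8, so the SAP plans change where an OCT quantity is handled as a number. The subtraction in 7.3.1 cannot be applied to categories. For a categorical field, protocol 7.2 and 7.2.5 are largely met by frequency tables. This is a reasonable inference, and it is why the departure from the protocol is stated only as a condition.

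It does not remove the mismatch between 6.4 and 7.6, because change in a category can be shown by a shift table.

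Other points also stand in part. A category could itself express change against Visit 01, but nothing in the documents says so. Net change in the group can be seen from the frequencies, within the limits shown above. Listing 12.2.6.3 should let a reader trace single eyes if it includes OCT, though a listing is not a summary. The lack of an OCT shift-table title in the appendix carries little weight, since that list is adaptable and has no separate change table for the other three parameters either.

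**Conclusion.** The concern holds: SAP 7.6 does not analyse optic-nerve OCT as the change variable that SAP 6.4 defines. It is worth correcting, but its weight is minor. The objective is secondary and exploratory, there are at most 26 subjects, and the other three parameters keep change over time.

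The loss depends on facts not in the documents: the OCT categories, whether values are numeric, and how many eyes drop out or revert. It ranges from nothing (no drop-outs and no reversals, or categories that already express change) to an uncertainty of a few eyes in the illustration, or to the absence of any mean change if the data are numeric. A departure from the protocol is not established.

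**What to change.** In SAP 7.6, add one of two forms for optic-nerve OCT, by eye and visit, and state which applies:

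- where RNFLT or BMO-MRW was recorded numerically, raw value and change from Visit 01;
- where only categories were recorded, shift tables from Visit 01 to each later visit.

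Base change and shifts on eyes assessed at both visits, and show missing results separately. If the chosen form differs from protocol 7.2.5, say so and justify it in the SAP text. If the recorded categories already express change against Visit 01, state that; the frequencies can then stay as they are.

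The cost is SAP wording and a few descriptive tables from data already collected; no scan has to be re-read. One drawback is that sites use their own devices (protocol 6.1.2), so pooled thickness values may be heterogeneous. Change within an eye on one device is less affected, but the protocol's advice against changing the OCT device appears only under anterior-segment OCT (6.4.4.13).

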### Changes in glaucoma medication

Any glaucoma medication with a start date at or after first visit (V01) will be regarded as new and/or changed glaucoma medication. Analysis for incidence rates of changes in glaucoma medication will be performed analogue to the analysis for incidence rates of AEs (see Section 7.7). The rate of changes in medication per 10 patient years and accompanying exact 95% confidence intervals will be calculated, assuming that the number of such events is Poisson distributed.

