	
 • Optical coherence tomography (OCT) of cornea and anterior chamber • Corneal endothelial cell density measurement • Gonioscopy 
Posterior segment
 
 • Funduscopy • Optical coherence tomography (OCT) of macula and optic nerve • Fundus photography 
IOP measurement
 
 • Goldmann Applanation Tonometry (GAT) • Pascal DCT tonometry • ARGOS-IO measurements 
Semiannual Follow-up (V02-V07)
 
The examinations performed at each visit are listed without mentioning the single visit in parentheses. Examinations that are carried out only at distinct visits are indicated in parentheses. The follow-up visits will include:
 
General
 
 • ADE/SAE/SADE • Device deficiency • Concomitant medication • Glaucoma medication • BCVA (EDTRS) • Perimetry • National Eye Institute Questionnaire – VFQ-25 (V03, V05 and V07) • Check patient diary for completeness 
Anterior Segment
 
 • External eye photography (slit-lamp), including iris retroillumination • Slit-lamp biomicroscopy • Optical coherence tomography (OCT) of cornea and anterior chamber • Corneal endothelial cell density measurement • Gonioscopy 
Posterior segment measurement
 
 • Funduscopy • Optical coherence tomography (OCT) of macula and optic nerve

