5.1.2 Secondary Objectives

- Evaluating the patient's compliance in IOP self-monitoring
 - Daily self-measurements with the ARGOS-IO sensor should be done at least 4 times daily (morning, noon, afternoon, evening)
- Evaluating the impact of IOP self-monitoring on glaucoma progression
 - Parameters to evaluate the glaucoma progression are visual field, cup/disc ratio, OCT of the optic nerve and the IOP.
- Evaluation of incidence in glaucoma medication change
- Evaluation of number of unscheduled visits due to self-measured increased intraocular pressure
 - The patients decide to come for a visit by their own due to any reason. This will be documented.

 Implantata Ophthalmic Products GmbH	Clinical Investigation Plan ARGOS-03	Revision C Page 28 of 67
--------------------------------------------------------------------------------------------------------------------------	-------------------------------------------------	---------------------------------

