6.4.4 Assessments

6.4.4.1 *Patient Demographics/other Baseline Characteristics*

Patient demographic and baseline characteristic data to be collected on all subjects include: year of birth, sex, race, weight, height and educational level

6.4.4.2 *Comparative Measurements*

All ARGOS-IO measurements which were performed in the clinic between study end of the ARGOS-01/ARGOS-02 trial and which have a comparative GAT measurement should be entered in the eCRF.

6.4.4.3 *Medical History*

Relevant medical history/current medical condition data includes data five years back until start of the study and everything what is important of the investigator's point of view. Relevant medical history should be supplemented by review of the subject's medical chart and/or by documented dialog with the subject's referring physician. If possible, diagnoses and not symptoms are to be recorded.

6.4.4.4 *Concomitant Medication, Treatments and Devices*

There are no restrictions for the use of concomitant medications and treatments required for ophthalmological or systemic diseases during this clinical trial. The use of concomitant medication and treatments will be documented in the patient's file and in the CRF.

6.4.4.5 *ADEs/SAEs/SADEs*

All ADEs/SAE/SADEs will be recorded.

6.4.4.6 *Check of functionality of the Mesograph and Multiline Connector*

At V01, the Mesograph will be tested for no error messages, enough storage and filled charged battery. The Multiline Connector will be tested for proper data transmission. If necessary, the devices will be changed.

6.4.4.7 *Confirmation of the correct function of the ARGOS-IO sensor*

The correct function of the ARGOS-IO implant must be confirmed using GAT (the average of 3 EYEMATE-IO measurements are compared to one GAT measurement), and adjusted if necessary (please refer to the *Mesograph IFU* for details).

 Implantata Ophthalmic Products GmbH	Clinical Investigation Plan ARGOS-03	Revision C Page 34 of 67
--------------------------------------------------------------------------------------------------------------------------	-------------------------------------------------------	---------------------------------

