7.1.5 Secondary Outcome Variables

- Progression of visual field, cup/disc ratio, OCT results for the optic nerve and IOP over the course of the study.
- Number of changes in glaucoma medication.
- Number of unscheduled visits due to self-measured increased IOP.

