### 3.1 Date Coding and Day Numbering

The format for presentation of date variables will be DDMMYY YYYY. The format for presentation of time variables will be hh:mm.

Missing or incomplete dates will not be completed. For additional considerations towards the time allocation of diseases and therapies, refer to Sections 3.2.2 and 3.2.4.

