### 7.4.3 Medical History, Concomitant Diseases and Concomitant Medications

Absolute and relative frequencies (n, %) of medical history and concomitant diseases will be described based on MedDRA system organ class (SOC) and preferred term (PT) levels by related body system. Results will be prepared by frequency of occurrence.

Absolute and relative frequencies (n, %) of concomitant medication will be provided based on Anatomical Therapeutic Chemical (ATC) Classification code levels 2 and 3 separately for glaucoma medication and other medications. Only medications ongoing at screening or with start date during the study will be considered, all other medications will be listed only.

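### SAP 7.6 counts glaucoma medication changes by start date alone, so the reported rate of changes is a rate of new starts and leaves out medications stopped without replacement

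*SAP*

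**What the plan says.** The objective is worded almost identically in the two documents: "Evaluation of incidence in glaucoma medication change" (protocol 5.1.2) and "Evaluation of incidences in glaucoma medication change" (SAP 2.4.3). The variable in protocol 7.1.5 is "Number of changes in glaucoma medication", and SAP 6.4 repeats it. None of these says that only additions count.

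Protocol 7.2.5 says how changes are to be analysed (a Poisson rate per 10 patient-years with an exact 95% confidence interval) but does not define a change. The definition comes in SAP 7.6: "Any glaucoma medication with a start date at or after first visit (V01) will be regarded as new and/or changed glaucoma medication". The number of such records is then turned into a rate in the same way as the adverse event rates of SAP 7.7.

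For the descriptive medication table, SAP 7.4.3 states: "Only medications ongoing at screening or with start date during the study will be considered". The SAP appendix also lists a summary of changes (Table 8.2.4.1), a table of changes per 10 patient-years (Table 8.2.4.2) and a listing of glaucoma medication (Listing 12.2.5.1).

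**The concern.** The label and the rule measure different things. A change can be an addition, a switch or a stop. A rule based on start dates captures the first two and has no way to register the third. A patient whose only change during the study was to come off an agent contributes exposure to the denominator and nothing to the numerator.

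The study wants to learn what happens to treatment when patients can measure their own pressure. Protocol 4.3 expects this to allow finer adjustment of treatment. A figure that cannot show an agent being dropped describes only part of that, yet its title tells the reader that it covers all changes. The exact confidence interval does not help: it describes chance variation in the counted starts, not the events the definition leaves out.

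**Working it through.** The documents state no expected number or rate of medication changes, so there is no planned figure to reproduce. The check has three parts.

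**1. Apply the SAP 7.6 rule to each kind of change.**

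| Change during the study | Events counted |
|---|---|
| New agent added | 1 |
| Agent A replaced by agent B | 1 (the start of B) |
| Agent ongoing at V01, stopped without replacement | 0 |
| Agent started after V01, later stopped without replacement | 1 (the start; the stop adds 0) |
| Dose change | 1 if entered as a new record with a new start date, otherwise 0; the documents do not state the convention |

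**2. Look for another output that would show stops.**

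- The SAP 7.4.3 table counts agents ongoing at screening or started on study. An agent stopped later still appears there as used.
- Listing 12.2.5.1 shows individual records but no rate.
- Tables 8.2.4.1 and 8.2.4.2 carry no definition of their own. The only definition they can draw on is the one in SAP 7.6.

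**3. Size of one omitted stop.**

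Inputs: at most 26 patients (5 + 21; protocol 7.2.7, SAP 2.9), V07 at day 1080 with a window of 3 weeks either way (SAP 2.3), and rates per 10 patient-years (SAP 7.6). I take exposure as V01 to V07 with no drop-out, and 365.25 days to a year.

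- Patient-years = 26 × 1080 / 365.25 = 76.88
- One event = 10 / 76.88 = 0.130 per 10 patient-years
- V07 three weeks late for everyone: 26 × 1101 / 365.25 = 78.37, so 10 / 78.37 = 0.128
- V07 three weeks early for everyone: 26 × 1059 / 365.25 = 75.38, so 10 / 75.38 = 0.133
- 20 patients with full follow-up (assumed): 20 × 1080 / 365.25 = 59.14, so 10 / 59.14 = 0.169

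With S starts and D stops without replacement, the share of all changes left out is D / (S + D). The counts below are assumed for display and do not come from the documents. The intervals are exact Poisson: chi-square(0.025; 2k)/2 to chi-square(0.975; 2k + 2)/2, multiplied by 10 / 76.88.

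| Starts | Stops without replacement | Rate under SAP 7.6 (95% CI) | Rate with stops included (95% CI) | Share left out |
|---|---|---|---|---|
| 10 | 2 | 1.30 (0.62 to 2.39) | 1.56 (0.81 to 2.73) | 2/12 = 17% |
| 10 | 5 | 1.30 (0.62 to 2.39) | 1.95 (1.09 to 3.22) | 5/15 = 33% |
| 0 | 5 | 0.00 (0.00 to 0.48) | 0.65 (0.21 to 1.52) | 5/5 = 100% |

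The two rate columns use different event definitions, so the intervals should not be compared as if they estimated the same quantity.

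**The case against.** Four arguments can be made for the plan.

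*The protocol never defined a change.* Protocol 7 and 7.2 leave details and calculated variables to the SAP, and SAP 7.6 supplies the definition openly. This stands. A reader might infer an undeclared departure from the protocol because SAP 8 lists only the adaptation of the pressure analysis. The documents do not support that, since there was no protocol definition to depart from. What remains is a label that does not match its content.

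*The rule does not contain the word only.* That is true, but neither document offers a second rule, so a programmer has nothing else to apply.

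*The reported rate need not be too low.* A reader might infer that leaving out stops must understate the rate. Taken alone, the omission does lower the count. But SAP 7.6 fixes no counting unit. Two products started on one date, or a dose change re-entered as a new record, may each count, and each extra start adds the same 0.13 that an omitted stop removes. The net sign cannot be derived.

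*Stop dates may not be available.* No passage states that they are recorded. On the other side, the protocol synopsis lists glaucoma medication among the follow-up items with no visit restriction, under the convention "The examinations performed at each visit are listed without mentioning the single visit in parentheses". Protocol 6.4.4.4 adds: "The use of concomitant medication and treatments will be documented". The reference in SAP 7.4.3 to medication ongoing at screening implies that some status or end date exists. Protocol 6.5.2 and Table 1, however, name only concomitant medications. The fix therefore needs a fallback.

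Incomplete dates are a lesser matter. SAP 3.1 says "Missing or incomplete dates will not be completed", but the query process in SAP 5.1 and the case-by-case evaluation in SAP 5.4 cover most of it.

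**Conclusion.** The point holds as a mismatch between name and content. The rate of changes planned in SAP 7.6 is a rate of newly started glaucoma medications. Medications stopped without replacement are excluded by definition, and no other planned table reports a rate for them.

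Each omitted stop is worth about 0.13 per 10 patient-years at the nominal maximum exposure (0.128 to 0.133 across the V07 window; more with less follow-up). The number of such stops is unknown. A reader might also infer from the illustration that the rate of all changes would fall outside the reported interval. That depends wholly on assumed counts, and the documents give no basis for it.

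The variable is secondary and descriptive. No hypothesis test, power statement or primary result is affected. The correction is worth making because the output would otherwise be read as something it is not.

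**What to change.** In SAP 7.6:

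1. Keep the count of glaucoma medications with a start date at or after V01, and label it newly started glaucoma medications.
2. Add a count of glaucoma medications stopped on or after V01 without replacement. Exclude records closed only because participation ended.
3. Report total changes as the starts plus the stops without replacement, so that a switch counts once, through its new start.
4. Give all three as rates per 10 patient-years with exact 95% confidence intervals, and state that Tables 8.2.4.1 and 8.2.4.2 use these definitions.
5. Before hard lock, define replacement and the counting unit. The definitions should cover several starts on one date, a new agent that overlaps the old one, a short course begun and ended on study, and an interruption followed by resumption.

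If stop dates prove not to be recorded, date a stop to the interval between the two visits that bracket it. Alternatively, report starts only, name the variable newly started glaucoma medications, and state that discontinuations are not counted.

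The cost is SAP wording, one extra derivation and a review of incomplete stop dates. If stop dates exist, no new data collection is needed. SAP 2.11 already provides for documenting such a change before database close. This concerns counting only and implies nothing about how patients should be treated.
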